8.1.2. Blood Phosphatidylethanol Levels

Hepatic ethanol oxidation is the prevalent route of human ethanol metabolism, eliminating more than 90% of ingested ethanol. Several nonoxidative routes of ethanol metabolism that result in the enzymatic conjugation of ethanol to endogenous metabolites have also been described. Due to slower elimination rates, these nonoxidative ethanol metabolites persist in body fluids and tissues for much longer than ethanol itself, thus enabling the retrospective assessment of ethanol intake even when ethanol itself is no longer present in the body.

Phosphatidylethanol (PEth) is a phospholipid produced in erythrocyte membranes after alcohol exposure, first described by Alling et al. ([1983](#)). In drinking experiments, PEth production began as soon as ethanol was consumed and peaked 1 to 3 hours after alcohol consumption ([Gnann et al., 2012](#); [Heier et al., 2016](#)). With frequent alcohol consumption, and a half-life of approximately 5 days, PEth accumulates in whole blood ([Javors et al., 2016](#)). Because PEth can be detected in blood for up to one month after one-time alcohol intake, it can be used as a biomarker to determine both current and recent consumption ([Kummer et al., 2016](#)).

Ulwelling & Smith ([2018](#)) proposed 3 ranges of PEth values likely to describe a person's average recent alcohol consumption/drinking behavior:

- <20 ng/mL Abstinence or light drinking (0 to <2 drinks/day)
- 20 – 199 ng/mL Moderate drinking (2 to 4 drinks/day for several days a week)
- > 200 ng/mL Heavy drinking (at least 4 drinks/day for several days a week)

Thus, PEth may be used to identify and/or monitor individuals with chronic excessive drinking behavior ([Viel et al., 2012](#)).

8.2. Safety Assessments

Planned time points for all safety assessments are provided in the SoA ([Section 1.3](#)). Safety assessments will be conducted in all participants at every study visit unless otherwise specified.

Site personnel will be provided training in the use of all study-specific instruments (see the Study Reference Manual).

8.2.1. Screening Tests

All screening evaluations must be completed and reviewed to confirm that potential participants meet all eligibility criteria. The Investigator will maintain a screening log to record details of all participants screened and to confirm eligibility or record reasons for screening failure, as applicable.

8.2.1.1. Mini-International Neuropsychiatric Interview

The MINI Screen is a brief structured diagnostic interview to meet the need for a short but accurate structured psychiatric interview for multicenter clinical trials ([Sheehan et al., 1998](#)). This validated tool can be administered in a short period of time (approximately 15 minutes) and will be administered at screening to exclude participants with major psychiatric disorders. The MINI Screen will be administered by a Health Care Provider.

8.2.1.2. Laboratory Tests to Determine Eligibility

In addition to the hematology, clinical chemistry, coagulation, and urinalysis panels indicated in [Table 6](#), the following tests will be performed during screening:

- Follicle-stimulating hormone (as needed to confirm menopausal status)
- Viral serology (human immunodeficiency virus antibody, hepatitis B surface antigen, and hepatitis C virus antibody)
- Hemoglobin A_{1c}
- Urine drug screen (to include, at a minimum, amphetamines, barbiturates, cocaine, opiates, and benzodiazepines)

8.2.2. Physical Examinations

Complete physical examinations will be conducted at every visit. Physical examinations will include, at a minimum, assessments of the Cardiovascular, Respiratory, Gastrointestinal, Neurological, and Skin systems. Height will be measured and recorded at Screening. Weight will be measured and recorded at every visit.

- Investigators should pay special attention to clinical signs related to previous serious illnesses or AEs.
- All physical examinations should include inspection of the injection site.

8.2.3. Vital Signs

Temperature by skin refraction, pulse rate, respiratory rate, and blood pressure will be assessed, unless otherwise indicated in the SoA.

Blood pressure and pulse measurements will be assessed in the seated position with a completely automated device. Manual techniques will be used only if an automated device is not available.

Blood pressure and pulse measurements should be preceded by at least 5 minutes of rest for the participant in a quiet setting without distractions (e.g., television, cell phones).

Temperature will be obtained in degrees Celsius (°C), pulse rate will be counted for a full minute and recorded in beats per minute, and respirations will be counted for a full minute and recorded in breaths per minute.

Note: In addition to standard vital sign measurements for safety, vital signs will be recorded as part of the EIA and results will be identified as such (e.g., HR for EIA) in the eCRF

8.2.4. Electrocardiograms

Standard 12-lead ECGs will be performed in the supine position after the participant has rested comfortably for 5 minutes. ECGs will be obtained using an ECG machine that automatically calculates the heart rate and measures PR, QRS, QT, and corrected QT interval (QTcF, Fridericia correction). Refer to [Section 7.3.3](#) for QTc withdrawal criteria and any additional readings that may be necessary. Screening ECGs may not be repeated for determination of eligibility.

The Investigator or designee is responsible for reviewing the ECGs to assess whether the results are within normal limits and to determine the clinical significance of the results. These assessments will be recorded on the CRF.

ECGs also will be conducted for EIA assessments. These ECG results will be recorded as part of the EIA and will be identified as such (e.g., ECG for EIA) in the CRF.

Note: If multiple assessments are due, the order of priority should be ECG, vitals, blood draws, and then other assessments, with the PK sampling being performed preferably at the nominal time point.

8.2.5. Suicidal Ideation and Behavior Risk Monitoring

Patients diagnosed with AUD may be at risk for SIB. Because DCR-AUD is being developed for the treatment of AUD, HV will be screened and monitored for the presence or emergence of SIB while on study. Consideration should be given to discontinuing study intervention in participants who experience signs of SIB, following a risk assessment.

8.2.5.1. Columbia-Suicide Severity Rating Scale

The C-SSRS is a suicidal ideation rating scale created by researchers at Columbia University ([Posner et al., 2011](#)). It rates an individual's degree of suicidal ideation on a scale, ranging from "wish to be dead" to "active suicidal ideation with specific plan and intent."

The scale identifies behaviors that may be indicative of an individual's intent to commit suicide. The C-SSRS is used extensively across primary care, clinical practice, surveillance, research, and institutional settings and is part of a national and international public health initiative involving the assessment of suicidal ideation and behavior. The C-SSRS requires no mental health or medical training to administer it. The C-SSRS will be administered by site personnel who are trained in its administration.

The Baseline version will be administered at Screening and at subsequent visits the "C-SSRS Since Last Visit" version will be administered.

8.2.6. Clinical Safety Laboratory Assessments

See [Section 10.2](#) for the list of clinical laboratory tests to be performed and the SoAs ([Section 1.3](#)) for the timing and frequency.

The Investigator must review the laboratory report, document this review in the eCRF, and record any clinically relevant changes occurring during the study in the AE section of the eCRF. The laboratory reports must be filed with the source documents.

All laboratory tests with values considered clinically significantly abnormal during participation in the study should be repeated (central laboratory) until the values return to normal or stabilize at a level no longer considered clinically significant by the Investigator or Medical Monitor.

- If such values do not return to normal/baseline within a period of time judged reasonable by the Investigator, the etiology should be identified, and the Sponsor notified.
- All protocol-required laboratory assessments, as defined in [Section 10.2](#), must be conducted in accordance with the Laboratory Manual and the SoA ([Section 1.3](#)).
- If laboratory values from non-protocol specified laboratory assessments performed at the institution's local laboratory require a change in participant management or are considered clinically significant by the Investigator (e.g., SAE or AE), then the results must be recorded in the eCRF.

8.2.7. Pregnancy Testing

WOCBP should only be included after a confirmed menstrual period and a negative highly sensitive urine or serum pregnancy test. If a urine test is positive, it must be confirmed with a serum test. See [Section 8.3.5](#) for reporting of pregnancy in a study participant or the partner of a male participant.

Additional pregnancy testing should be performed as indicated in SoA ([Section 1.3](#)).

Pregnancy testing will be performed whenever a menstrual cycle is missed or when pregnancy is otherwise suspected.

Pregnancy testing with a sensitivity of at least 25 mIU/mL will be performed.

8.3. Adverse Events, Serious Adverse Events, and Other Safety Reporting

The definitions of AEs, SAEs, and adverse events of special interest (AESI) can be found in [Section 10.3.1](#), [Section 10.3.2](#), and [Section 10.3.3](#), respectively.

The Investigator and any qualified designees are responsible for detecting, documenting, and recording events that meet the definition of an AE or SAE and remain responsible for following up AEs that are severe or serious, and considered related to the study intervention or study procedures, or that caused the participant to discontinue study intervention or the study.

8.3.1. Time Period and Frequency for Collecting Adverse Event Information

All AEs and SAEs will be collected from the time the ICF is signed through the last follow-up visit at the time points specified in the SoAs ([Section 1.3](#)).

All SAEs will be recorded and reported to the Sponsor or designee within 24 hours, as indicated in [Section 10.3.5](#). The Investigator will submit any updated SAE data to the Sponsor within 24 hours of it being available.

Investigators are not obligated to actively seek AE or SAE after conclusion of study participation. However, if the Investigator learns of any SAE, including a death, at any time after a participant has been discharged from the study, and he/she considers the event to be reasonably related to the study intervention or study participation, the Investigator must promptly notify the Sponsor.

8.3.2. Method of Detecting AEs and SAEs

The method of recording, evaluating, and assessing causality of AE and SAE and the procedures for completing and transmitting SAE reports are provided in [Section 10.3](#).

Care will be taken not to introduce bias when detecting AEs and/or SAEs. Open-ended and non-leading verbal questioning of the participant is the preferred method to inquire about AE occurrences.

Injection sites will be examined by study staff for assessment of ISRs ([Section 10.3.3](#)).

8.3.3. Follow-up of AEs and SAEs

After the initial AE/SAE report, the Investigator is required to proactively follow each participant at subsequent visits/contacts. All SAEs and AESIs (as defined in [Section 10.3.3](#)), will be followed until resolution, stabilization, the event is otherwise explained, or the participant is lost to follow-up (as defined in [Section 7.2](#)). Further information on follow-up procedures is provided in [Section 10.3.4](#). If symptoms related to ethanol ingestion that the Investigator considers relevant are present at the end of study, the Sponsor may request continued contact with participants in order to collect further data.

8.3.4. Regulatory Reporting Requirements for SAEs

Prompt notification by the Investigator to the Sponsor of an SAE is essential so that legal obligations and ethical responsibilities towards the safety of participants and the safety of a study intervention under clinical investigation are met.

The Sponsor has a legal responsibility to notify both the local regulatory authority and other regulatory agencies about the safety of a study intervention under clinical investigation. The Sponsor will comply with country-specific regulatory requirements relating to safety reporting to the regulatory authority, IRBs/IECs, and Investigators.

Investigator safety reports must be prepared for suspected unexpected serious adverse reactions (SUSAR) according to local regulatory requirements and Sponsor policy and forwarded to Investigators as necessary.

An Investigator who receives an Investigator safety report describing a SAE or other specific safety information (e.g., summary or listing of SAEs) from the Sponsor will review and then file

it with the Investigator's Brochure and will notify the IRB/IEC, if appropriate, according to local requirements.

8.3.5. Pregnancy

Details of all pregnancies in female participants and female partners of male participants will be collected after the start of study intervention and until 24 weeks after the last dose.

If a pregnancy is reported, the Investigator should inform the Sponsor within 24 hours of learning of the pregnancy and should follow the procedures outlined in [Section 10.4.3](#).

While pregnancy itself is not considered to be an AE or SAE, any pregnancy complication or elective termination of a pregnancy for medical reasons will be reported as an AE or SAE. Abnormal pregnancy outcomes (e.g., spontaneous abortion, fetal death, stillbirth, congenital anomalies, ectopic pregnancy) are considered SAEs.

The participant or pregnant partner will be followed to determine the outcome of the pregnancy. The Investigator will collect follow-up information on the participant or pregnant partner and the neonate, and the information will be forwarded to the Sponsor.

Any post-study pregnancy-related SAE considered reasonably related to the study intervention by the Investigator will be reported to the Sponsor as described in [Section 8.3.4](#). While the Investigator is not obligated to actively seek this information in former study participants, he or she may learn of an SAE through spontaneous reporting.

8.4. Treatment of Overdose

For this study, any dose of DCR-AUD greater than 960 mg will be considered an overdose.

The Sponsor does not recommend specific treatment for an overdose.

In the event of an overdose, the Investigator should:

- Keep the participant under observation at least overnight. The Investigator will use his or her judgment to determine if it is safe for the participant to undergo the EIA scheduled for that visit.
- Closely monitor the participant for any AEs or laboratory abnormalities until DCR-AUD PD effects can no longer be detected.
- Contact the CRO Medical Monitor immediately.
- Document the quantity of the excess dose.

It should be noted that an overdose is not an AE, in and of itself. See [Section 10.3.1](#) for details.

8.5. Pharmacokinetics

Blood samples (2 mL) will be collected for measurement of plasma concentrations of DCR-AUD and its metabolites as specified in the SoAs (see [Section 1.3](#)).

Instructions for the collection and handling of biological samples will be provided by the Sponsor in the Laboratory Manual and the Laboratory Specification document. The actual date and time (24-hour clock time) of each sample will be recorded.

Each plasma sample will be divided into 2 aliquots (one for PK and one backup). Samples collected for analyses of plasma concentrations of DCR-AUD and its metabolites may also be used to evaluate safety or efficacy aspects related to concerns arising during or after the study.

Pharmacokinetic parameters to be determined may include area under the concentration curve (AUC), minimum observed concentration (C_{min}), maximum observed concentration (C_{max}), time to maximum concentration (T_{max}), terminal elimination half-life ($t_{1/2}$), apparent clearance (CL/F), and apparent volume of distribution (Vd/F). Additional parameters may be estimated if deemed appropriate.

Any changes in the timing or addition of time points for any planned study assessments must be documented and approved by the relevant study team member and then archived in the Sponsor and site study files but will not constitute a protocol amendment. The IRB/IEC will be informed of any safety issues that require alteration of the safety monitoring scheme or amendment of the ICF.

Drug concentration information that may be unblinding will not be reported to investigative sites or blinded personnel until the study has been unblinded.

8.6. Pharmacodynamics

DCR-AUD is designed to selectively reduce ALDH2 activity in the liver and the conversion of acetaldehyde to acetic acid after alcohol consumption. The build-up of acetaldehyde causes unpleasant effects after drinking (e.g., flushing, headache, lightheadedness, palpitations, nausea, or vomiting). As such, the PD activity of DCR-AUD will be assessed during EIAs via these 6 symptoms, blood biomarkers (ethanol, acetaldehyde, and acetate), and heart rate.

Published literature consistently demonstrate that administration of low/moderate alcohol intake (0.1 to 0.8 g/kg) in human *ALDH2* mutation homo- or heterozygotes results in clearly differentiated increases in blood acetaldehyde and heart rate compared with ALDH2 normal alleotypic controls ([Bae et al., 2012](#); [Peng et al., 1999](#); [Peng et al., 2007](#); [Nishimura et al., 2002](#); [Enomoto et al., 1991](#)).

8.6.1. Ethanol Interaction Assessments

Serial EIAs will be performed to assess the indirect PD effects of ALDH2 reduction (acetaldehyde increase). EIAs will be conducted in accordance with the SoA in [Section 1.3](#). Should an EIA be missed, due to COVID-19 or other circumstances, the missed EIA may be conducted at an unscheduled visit at the discretion of the Investigator and the Sponsor.

Participants will be required to be fasted for at least 3 hours prior to administration of a standardized meal and must have a negative breath alcohol test on the day of the study visit prior to the EIA. Prior to each EIA, venous catheters will be placed at least 20 minutes before the first EIA vital signs are assessed at time 0. For EIAs conducted prior to a dosing day, the venous catheter will be left in place for PK sample collections.

Participants will consume a fixed dose of ethanol mixed in a liquid that has no additional alcohol, no caffeine, and is low in sugar. The ethanol dose will be 0.8 g/kg (to a maximum of 56 g) for male participants and 0.68 g/kg (to a maximum of 48 g) for female participants. Ethanol will be consumed in 4 equal aliquots over an 80-minute period (20 minutes for each

aliquot). During the EIA, participants will receive nothing by mouth (remain NPO) except water ad libitum. Assessments will be made over an estimated 4-hour period, as detailed in [Table 3](#).

Participants will remain in the Phase 1 unit for over-night observation. The Investigator will not discharge any participant experiencing ongoing effects of ethanol administration and will not do so until it is deemed medically safe to do so.

8.6.1.1. EIA Blood Biomarkers

Blood biomarkers to be assessed include measurement of acetaldehyde, acetate, and ethanol. Blood samples (2 mL) will be collected via a venous access device at the times indicated in [Table 3](#). Additional details regarding blood sample collection and processing will be detailed in the Laboratory Manual.

As plasma biomarker data may be unblinding, results will not be reported to investigative sites or blinded personnel until the study has been unblinded.

8.6.1.2. EIA Physiologic Signs and Symptoms

EIA assessments will include the direct questioning of participants as to the presence of ethanol reaction symptoms (flushing, headache, lightheadedness, palpitations, nausea, and vomiting) at the times indicated in [Table 3](#). Note: the presence of these ethanol reaction symptoms will not be considered AEs.

A composite 6-symptom score for each participant during each EIA will be determined as follows:

- At each of the timepoints during the EIA, each symptom will be given a numeric score of 0 (not present) to 3 (present and severe), with the exception of vomiting, which will be given a score of 3.
- The composite symptom score for each of the EIA timepoints will be the summed value for each of the 6 symptoms at that timepoint (range 0 – 18).
- The Peak score for a given day's EIA will be the participant's highest post-alcohol ingestion timepoint score minus the participant's pre-alcohol score.

Vital signs (BP and heart rate) and standard 12-lead ECGs will be recorded at the times indicated in [Table 3](#).

8.6.1.3. Stopping Rules for an EIA

During the conduct of an EIA, administration of alcohol to a participant may be stopped for the following physiologic responses, though follow-up EIA assessments will be conducted:

- Any vomiting or severe nausea (as judged by Investigator)
- Systolic blood pressure increase of > 25 mmHg (or to a level > 160 mmHg) or decrease of > 15 mmHg to < 70 mmHg or any decline accompanied by symptomatic hypotension (pre-syncope, syncope, lightheadedness)
- Diastolic blood pressure decrease to < 50 mmHg or any decline accompanied by symptomatic hypotension (pre-syncope, syncope, lightheadedness)

- HR increase of > 20 beats per minute and to a level > 100 beats per minute
- Temperature increase of > 1°Celsius
- Any clinically meaningful change in affect or clinical status, per Investigator or supervising designee's clinical judgment

8.6.1.4. Follow-up of Participants Who Continue to have Positive Ethanol Reaction Symptoms at Day 168 (Conditional Follow-up)

All participants who have ethanol reaction symptoms during the Day 168 EIA will be instructed to continue limit drinking to 4 drinks or less during any drinking session.

Participants who present clinically significant positive ethanol reaction symptoms at the Day 168 EIA (flushing, headache, lightheadedness, palpitations, nausea, or vomiting) that the PI considers severe and/or warranting further follow-up, will be followed for an additional 4 weeks (through Day 197; see [Table 1](#)). If symptoms related to ethanol ingestion that the Investigator considers relevant are present at Day 197, the Sponsor may request continued contact with participants in order to collect further data.

8.6.2. Presence of Physiologic Symptoms Associated with Consumption of Ethanol Outside of EIAs

Participants will be allowed to continue drinking alcohol in the windows between study visits, but will be advised not to drink more than 4 drinks in any one drinking session. Participants will be given a diary to report the occurrence and severity of any physical symptoms that occur with alcohol consumption outside of the in-clinic EIAs.

Participants will be instructed to stop drinking at the onset of any symptoms during outside drinking sessions.

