5.3. Lifestyle Considerations

Alcohol, Tobacco, and Cannabis

1. Study participants are to refrain from drinking alcohol for 24 hours prior to each EIA and must have a negative breath-alcohol test on the day of the study visit.
2. Study participants will be advised to avoid consuming more than 4 drinks during any drinking session outside of in-clinic EIAs.
3. Study participants will be instructed to stop drinking at the onset of any ethanol reaction symptoms during outside drinking sessions.
4. Tobacco/nicotine use is not restricted.
5. Study participants are to refrain from using cannabis for 24 hours prior to each EIA and must have a negative urine-drug test on the day of the study visit.

Activity

1. Study participants should abstain from strenuous exercise for 24 hours before each blood collection for clinical laboratory tests. Participants may participate in light recreational activities (e.g., walking at a pace < 3 miles per hour, shopping, watering plants) in that 24-hour time period.

Meals and Dietary Restrictions

1. For each EIA study visit, participants will be required to fast for at least 3 hours and then will be fed a standardized meal in the clinic prior to administration of ETOH for the EIA.

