7.3.4. Significant Negative Reaction to Alcohol Ingestion

Any participant who experiences a significant negative reaction to alcohol ingestion that includes severe or serial vomiting or hemodynamic instability (syncope or significant pre-syncope, or BP decline of more than 25 mmHg from Baseline with some lightheaded symptoms, or HR increases to ≥ 110 bpm with some symptoms during an EIA) will be discontinued from additional dosing and will be advised to not drink outside of the clinic for the duration of the study. The participant will continue to be followed in the study for other protocol-specified procedures. The PI will determine if additional/subsequent protocol-specified EIAs will be conducted, based on the nature and severity of symptoms observed.

See [Section 8.6.1.3](#) regarding full details on stopping rules for conduct of an EIA.

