7.4. Study Stopping Rules

All further dosing in the study will be stopped if any of the following conditions occur AND the SRC recommends stopping the study:

- 2 participants develop a Grade 3 CTCAE event, unless it is clearly the result of a non-study-related event.
- 1 participant develops a \geq Grade 4 CTCAE event, unless it is clearly the result of a non-study-related event.

All further DCR-AUD dosing and subsequent EIAs will be stopped if the following occurs AND the SRC recommends stopping the study:

- 3 participants treated with DCR-AUD experience significant or severe adverse symptoms associated with alcohol ingestion. In the event this occurs, all study participants will be advised to avoid alcohol for the remainder of the study period.

In the event a study stopping rule is triggered and the SRC calls a halt on dosing, the SRC may request that an external, independent, unblinded DSMC be convened to review the decision and make a recommendation to the SRC as to whether the study should stop or continue with no changes or continue with appropriate modifications to address the safety concern (see [Section 10.1.5](#)). Should the DSMC recommend stopping the study, all ongoing participants will continue to be followed for safety assessments as indicated in the schedule of activities.

The Sponsor will promptly notify the site if study stopping rules are triggered.

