8.1. Efficacy Assessments

This is a Phase 1 study with the primary objective of evaluating safety. Pharmacokinetic and PD assessments are detailed in [Section 8.5](#) and [Section 8.6](#), respectively.

As the study participants are HV not diagnosed with AUD, no true assessment of efficacy can be made. However, study participants may be inclined to change their alcohol intake should they experience physiologic symptoms associated with increased acetaldehyde while drinking. As such, 2 assessments of alcohol intake, TLFB and PEth, will be considered in exploratory analyses.

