9.4.1. General Considerations

In general, summary statistics (n, mean, SD, median, minimum, and maximum for continuous variables, and number and percentage of participants in each category for categorical variables) will be provided for all variables.

Baseline is defined as the last non-missing measurement prior to the date and time of the dose of study intervention.

All analyses will be based on observed data without imputation for missing values. Except for outlier analyses, measurements collected from unscheduled visits will not be included in the summary tables or figures but will be included in the participant listings. Source data for the summary tables and statistical analyses will be presented as participant data listings.

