9.4.4. Exploratory Endpoint(s)

The exploratory endpoint of change in drinking amounts will be assessed using the TLFB and by analysis of blood levels of phosphatidylethanol.

Average daily drinking amounts over each 2-week period after the start of dosing will be compared to the amount during the 2-week period before first dose. Change in drinking amounts for each postdose period will be evaluated in connection with changes in EIA-induced peak symptoms and plasma acetaldehyde levels during the preceding EIA.

Other exploratory analyses will be conducted as deemed appropriate and will be detailed in the SAP.

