4.13.7.2 Exploratory Analyses

The descriptive statistics of participant’s alcohol consumption measured by TLFB will be present for each arm and study days. Each of the drinks will be multiplied by 14g to achieve the alcohol amount. [3]. Change of baseline from both day -1 and screening visit will be presented for each arm. The mean difference and its 95% CI will be presented for the change from baseline of alcohol consumption for each assessment day. Similar analysis will also be performed for total alcohol consumed from baseline.

For PEth descriptive statistics will be present for assessment days. The mean difference and its 95% CI will be presented for the change from baseline of PEth levels for each assessment day.

By participant listings will be present for the exploratory analyses for SP.

4.13.8 Daylight Saving Time (DST):

Not applicable.

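### The exploratory drinking-change displays include, unmarked, periods after participants have been advised to abstain, so part of any fall in drinking and of its link to EIA symptoms could be instructed

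*Protocol*

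**What the plan says.** TLFB and PEth are exploratory measures. Protocol 8.1 explains why they are collected: "study participants may be inclined to change their alcohol intake should they experience physiologic symptoms associated with increased acetaldehyde while drinking". That describes a participant's own choice.

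Three instructions bear on the same behaviour:

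- **Stop at symptom onset.** Protocol 5.3: "Study participants will be instructed to stop drinking at the onset of any ethanol reaction symptoms during outside drinking sessions". Protocol 8.6.2 repeats it: "Participants will be instructed to stop drinking at the onset of any symptoms during outside drinking sessions".
- **Individual abstinence advice.** Under Protocol 7.3.4, a participant with a significant negative reaction (severe or serial vomiting, or hemodynamic instability) "will be discontinued from additional dosing and will be advised to not drink outside of the clinic for the duration of the study". The participant stays in follow-up.
- **Study-level abstinence advice.** Under Protocol 7.4, if three DCR-AUD participants have significant or severe symptoms with alcohol and the SRC recommends stopping, dosing and EIAs stop. "In the event this occurs, all study participants will be advised to avoid alcohol for the remainder of the study period".

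On analysis, Protocol 9.4.4 compares each two-week post-dose period with the two weeks before first dose and adds: "Change in drinking amounts for each postdose period will be evaluated in connection with changes in EIA-induced peak symptoms and plasma acetaldehyde levels", taken from the preceding EIA. SAP 4.13.7.2 says "The mean difference and its 95% CI will be presented for the change from baseline of alcohol consumption for each assessment day" and plans the same for PEth. It does not carry the symptom relation forward, but SAP 4.21 declares no change to the planned analysis, so Protocol 9.4.4 stands. Protocol 9.4.1 sets the data rule: "All analyses will be based on observed data without imputation for missing values". SAP 4.16 to 4.18 (covariates, missing data, subgroups) are marked not applicable. No text mentions drinking recorded after abstinence advice.

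**The concern.** The event that triggers individual advice is closely tied to the variable that drinking change is related to. Vomiting scores 3 in the six-symptom composite (Protocol 8.6.1.2), and lightheadedness and palpitations are also components. Protocol 7.3.4 is triggered by severe or serial vomiting, by a blood-pressure fall with lightheaded symptoms, or by a high heart rate with symptoms. Those with the strongest EIA reactions are therefore the likeliest to be told not to drink. A relation between peak symptoms and falling consumption could then appear even if nobody chose to drink less.

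The placebo arm does not remove this. The advice follows reactions, and DCR-AUD is designed to cause them. At stake is how the study's only look at drinking behaviour is read. No primary or safety result is affected.

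**Working it through.** The plan gives no figure to reproduce: Protocol 9.2 and SAP 4.20 state that no formal sample size estimation was done. What follows is illustration.

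**Inputs from the documents.** 12 active and 4 placebo participants (Protocol 9.2); eligible baseline of 5 to 20 drinks per week for men and 5 to 14 for women (Protocol 5.1); 14 g per drink (SAP 4.13.7.2).

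**Shift in the arm mean.** Suppose k of 12 active participants abstain on advice, nobody else changes, and the abstainers had arm-average baseline B. The mean then changes by -k × B/12, which is k/12 of baseline.

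- k = 1: 1/12 = 8.3%. In drinks, 5/12 = 0.42 to 20/12 = 1.67 per week; at 14 g per drink, 5.8 to 23.3 g per week.
- k = 2: 2/12 = 16.7%.
- k = 3: 3/12 = 25%, or 1.25 to 5.0 drinks per week.
- One advised abstainer among 4 placebo participants: 1/4 = 25%.

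**Stop-at-onset instruction.** The documents do not say how much drinking this would remove. If it cut one active participant's drinking by 25% to 75%, the arm mean would fall by 0.25/12 = 2.1% to 0.75/12 = 6.3%. That is less per person than abstinence, and the total depends on how many are affected.

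**How likely a trigger is.** No reaction rate is given. For an assumed risk of 5% to 30% per participant, the binomial chance of at least one reaction in 12 is 46% to 99%, and of at least three is 2% to 75%. No clear PD effect was seen after single doses in the first-in-human study (Protocol 4.2), although the EIA ethanol dose there was half as large.

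**Induced association.** Simulation, 6,000 runs per setting, 16 participants, no systematic voluntary change. All inputs are assumptions except the arm sizes and the 5 to 20 range: baseline uniform on 5 to 20 drinks per week; spontaneous change with mean 0 and SD 2, 3 or 5, not below minus baseline; peak score Poisson(1.5) in non-reactors. Mean Pearson correlation between peak score and drinking change:

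| Setting for advised reactors | 0 reactors | 1 to 3 reactors |
|---|---|---|
| Scores 6 to 10, full abstinence | about 0 | -0.44 to -0.81 |
| Scores 3 to 6, full abstinence | about 0 | -0.29 to -0.64 |
| Scores 3 to 6, drinking halved | about 0 | about -0.17 to -0.56 |

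The sign is the same in every setting with a reactor; the size is set by the assumptions.

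**Confidence intervals.** In the first setting the within-arm 95% CI lay wholly below zero in 1.6% to 4.1% of runs with one abstainer, close to the nominal 2.5%, and in 12.4% to 17.5% with three. The distortion is mainly in point estimates and in the symptom relation.

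**Study-level rule.** If the Protocol 7.4 advice is given and followed, outside drinking falls to zero in both arms and the arms can no longer be told apart. EIAs also stop, so no new EIA is available for the Protocol 9.4.4 relation.

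**The case against.** Much of the case on the other side stands.

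- **The reductions are not called response.** A reader might infer that the plan counts instructed abstinence as response. Neither document defines a response. The objective is to explore change after treatment, and Protocol 8.1 says efficacy cannot truly be assessed in these volunteers. Describing all observed drinking is a legitimate treatment-policy choice; the plan simply does not say that it makes it.
- **The diary is not wholly unused.** A reader might infer this because the SAP names the diary only in its schedule of activities. But Protocol 8 gives the diary the purpose of tracking AEs from alcohol intake, and Protocol 10.3.1 excludes only symptoms solicited during EIAs from the AE definition. Symptoms from outside drinking can therefore reach the AE listings and tables of SAP 4.13.1.
- **Planned outputs are not blind to it.** By-participant listings of the exploratory data and individual peak EIA profiles are planned (SAP 4.13.7.2 and 4.12.1.1). With 16 participants they identify many of those affected. A reaction before Day 57 also shows as a missed dose. But five of the ten scheduled EIAs (Weeks 10, 12, 16, 20 and 24) come after the last dose, where that marker is absent, and a high EIA score does not show that advice was given.
- **No correlation is specified.** Protocol 9.4.4 only says that the two will be evaluated in connection, and Protocol 9.1 plans no inferential tests. The simulated coefficients illustrate a direction.
- **Some would have cut down anyway.** Someone with serial vomiting or near-syncope may stop unprompted. No analysis can separate the two motives in that person.

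What survives is that no output marks the advice, and that the advice alone can produce the pattern Protocol 9.4.4 looks for.

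**Conclusion.** The concern holds, conditionally. If significant reactions occur and the abstinence advice is followed, the TLFB and PEth displays and the Protocol 9.4.4 relation will mix instructed with voluntary reduction, and nothing planned marks which periods are affected. Each advised abstainer moves the active-arm mean by about 8%, given average baseline and full adherence. The induced correlation for one to three advised reactors is roughly -0.2 to -0.8, and its size rests on assumed scores and adherence.

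The documents do not support going further. The figures do not point to routine false significance: with one abstainer the confidence interval behaves almost nominally. The stop-at-onset instruction is a minor part of the point. If no reactions occur, nothing changes. The endpoint is exploratory, so the risk is a misread signal; a small SAP addition is still worth making.

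**What to change.** In SAP 4.13.7.2, descriptive only:

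1. State that the main TLFB and PEth displays include all observed drinking, whether or not the participant had been instructed to stop or abstain.
2. In the existing listings, flag participant-periods from the date of advice under Protocol 7.3.4 or 7.4 onward. The documents do not say whether that date is a database field; if it is not, use the date of the EIA or AE that triggered the advice.
3. Repeat the TLFB and PEth change, and the Protocol 9.4.4 relation to peak symptoms and acetaldehyde, without the flagged periods, labelled as a sensitivity display.

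Marking diary-reported symptoms, or adding a separate diary listing, is optional.

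The cost is a sentence, one flag and a second version of a few exploratory displays. No visit, test or protocol change is needed. The downside is that the second display drops participants selected for reacting, from arms of 12 and 4, and cannot say what they would have done without advice. It shows only how far the result depends on them. If the study-level advice is given, the second display ends for everyone at that date.
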